## **Protocol Summary**

**Full Title:** *Virtual vs Phone Education in Radiotherapy – Randomized Clinical Trial*

**Short Title:** *VIPER-RT*

**Study Type:** *Randomized Clinical Trial.*

**Sample Size:** *130 breast cancer patients. All radically treated breast cancer patients at the Radiation Therapy Department in Princess Margaret Cancer Center will be approached*

**Study Population:** *Breast cancer patients being treated with adjuvant breast radiotherapy at the Princess Margaret Cancer Centre (PMCC)*

**Accrual Period:** *7 months*

**Study Design:** *This study will employ a randomized clinical trial in which consented patients will be randomized into one of two groups for pre-treatment radiotherapeutic education. Patients will be placed into either the Control Group – Radiation Therapist led pre-treatment education using telephone calls as part of standard care, or the Intervention Group – Radiation Therapist led pre-treatment education using Microsoft Teams videoconferencing. Patients will be given a set of questionnaires prior to any education (T1), after their CT simulation appointment (T2) and at the end of their first radiation therapy treatment (T3) to assess effectiveness of education at reducing patients' procedural concerns, anxiety and overall satisfaction.*

**Study Duration:** *November 2025 to May 2026*

**Study Intervention:** *Pre-treatment radiotherapy education using video-conferencing software (i.e. Microsoft Teams)*

**Primary Objective:** *To compare whether the use of videoconferencing is more effective than telephone pre-treatment education at reducing breast cancer patients' procedural fears and concerns related to their radiation therapy treatment.*

**Secondary Objective:** *To compare whether the use of video-conferencing is more effective than telephone pre-treatment education at reducing patient reported anxiety levels.*

### **Endpoints of the study:**

- *Patient reported procedural fears and concerns measured by the Cancer Treatment Survey procedural fears and concerns subscale (CaTS-PC)*
- *Patient reported anxiety levels measured by Hospital Anxiety and Depression Scale anxiety subscale (HADS-A)*
- *Patient reported satisfaction with virtual care measured by survey adapted from Berlin et Al*

## **2.0 BACKGROUND INFORMATION**

### **2.1 Background**

Breast cancer (BC) is a major health concern worldwide. In 2024, it was stated that breast cancer makes up almost 25% of all new cancer diagnoses in women. Breast cancer was also found to be the leading cause of cancer death in women. The use of Radiation Therapy (RT) plays a major role in the treatment of breast cancer. Although RT has such a large role, the complexity of RT can be psychologically and physically demanding for patients. Many patients are provided with information by their oncologist at initial consultations; however, their information needs remain high before treatment planning and commencement. These same patients will seek out a large amount of information to help facilitate understanding of RT. In almost 50% of patients experience heightened anxiety and distress prior to radiotherapy, potentially resulting in longer daily treatments and worse treatment adherence.

A study comparing the use of two in-person radiation therapist led education sessions, one prior to CT-Simulation and the other prior to the first day of treatment found significantly lower levels of anxiety, depression and radiotherapy concerns post day 1 of radiation. Likewise, a study comparing the use of two medical physicist led education with radiotherapy patients prior to CT-Simulation and treatment to the standard radiation therapist led education session found statistically significant decreased anxiety levels, and increased patient technical satisfaction at the first treatment time point. Evidence from these studies suggests the use of pre-treatment education session led by a Radiation Therapist(s) can be beneficial to reduce patients' procedural fears, concerns and overall anxiety levels.

Due to the COVID-19 pandemic a significant transition to virtual appointments was done at Princess Margaret Cancer Centre. In the radiation therapy department specifically, the major shift was in pre-treatment education. The change resulted in all pre-treatment education appointments moving to telephone calls from in-person education., with the use of telephone calls has remaining as the standard since. Recently, evidence has come out to show the use of videoconferencing-based education having high levels of patient's satisfaction than that of telephone calls, as well as a larger patient preference for telephone calls. Recently a study by Maglizzi et al found the use of videoconferencing-based education demonstrated high levels of patient satisfaction and preference over telephone consultations.

### **2.2 Rationale for the study**

At our institution since the COVID 19 pandemic, restrictions to in-person activities are no longer in place. However practices for pre-treatment radiotherapy education with telephone calls have remained, largely as a convenience for staff and patients. Currently, evidence directly comparing these two modalities against each other is lacking.

### **2.2 Participant Risks and Benefits**

#### **2.2.1 Potential Risks and Risk Management**

There are no associated risks to patients in this study.

#### **2.2.2 Potential Benefits**

The main benefits include reduced radiation therapy related fears and concerns, and anxiety. Since use of videoconferencing allows for a face-to-face educational approach with patients with images and graphics to help facilitate patient understanding, that the use of telephone calls does not have. Patient informational needs and questions are more likely to be answered, resulting in less concerns and fears due to treatment and lower anxiety levels.

### **2.3 Study Population**

## VIPER-RT (Version 1.0)

Study population is limited to patients receiving radical breast cancer radiotherapy at the Princess Margaret Cancer Center. These patients must be 18 years of age or older, have access to an internet connected device with Microsoft Teams platform, and be able to communicate in English with or without the help of a hospital issued translator or caregiver.

### **3.0 STUDY OBJECTIVES AND HYPOTHESIS**

#### **3.1.1 Primary Objectives**

To determine whether the use of videoconferencing for pre-treatment education is more effective at reducing patient procedural fears and concerns.

#### **3.1.2 Secondary Objectives**

##### **3.1.2a Anxiety Levels**

To determine whether the use of videoconferencing for pre-treatment education is more effective at reducing patient anxiety levels in relation to radiotherapeutic treatment.

##### **3.1.2b Satisfaction**

To determine whether the use of videoconferencing for pre-treatment education has higher satisfaction levels than telephone calls.

#### **3.2 Study Hypothesis**

[figure not shown]
The use of videoconferencing for pre-treatment radiotherapy education will decrease breast cancer patients' procedural fears and concerns.

### **4.0 STUDY DESIGN**

This study will employ a single centre randomized clinical trial in which patients will be randomized into one of two groups. The study will have prospective longitudinal data collection via a set of questionnaires given at three time points. Time one (T1) baseline, Time two (T2) post CT simulation, and Time three (T3) after radiation treatment one. Participation in the questionnaires is mandatory for patients in the study population; however, patients are free to withdraw from the study at any points. An online or paper version of the questionnaires will be given to patients at each of the time points and will be collected by

## VIPER-RT (Version 1.0)

research team for data analysis. Patients will be reminded by their Radiation Therapists that they will have questionnaires to fill out before any of the appointments.

### 4.1 Endpoints

#### 4.1.1 Primary Endpoints

This will be measured using the Cancer Treatment Survey (CaTS) procedural fears and concerns subscale (CaTS-PC) at 3 time points, T1 baseline, T2 post CT Simulation and T3: post RT day 1. These measurements will be compared between the control and intervention group at each time point.

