## **7.0 STATISTICS**

A total sample of 116 patients (58 Telephone, 58 Videoconference), measured at 3 time points, will achieve 80% power at a 0.05 significance level to detect a 0.44 mean difference in Cancer Treatment Survey (CaTS) Procedural Concerns subscale scores between groups using a repeated measures design. The assumed standard deviation is 1.35, with a compound symmetry covariance structure and autocorrelation of 0.08. Based on the study by Halkett et al. (2018) for the same subscale score, the mean difference was derived from the estimate at the Prior to Treatment Planning (F1) time point, the assumed standard deviation is 25% lower than the estimated value of 1.80 from all confidence intervals, and the autocorrelation value was estimated from the reported Cohen's d at the Treatment completion (F3) time point. Anticipating a 10% dropout rate, the target recruitment sample is 130 (65 Telephone, 65 Videoconference). Sample size was calculated using PASS 2025, version 25.0.2.

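### The primary comparison is set at each of T1, T2 and T3, but the 80% power belongs to an average over all three visits, including pre-education T1; T2 or T3 alone has about 42%

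*Protocol*

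**What the plan says.** Section 4.1.1 (Primary Endpoints) measures CaTS-PC at "T1 baseline, T2 post CT Simulation and T3: post RT day 1" and adds: "These measurements will be compared between the control and intervention group at each time point". Neither that section, the primary objective (Protocol Summary and 3.1.1) nor the hypothesis (3.2) says which visit, or which combination of visits, answers the primary question.

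The Protocol Summary fixes the timing of T1: "Patients will be given a set of questionnaires prior to any education (T1", with T2 after CT simulation and T3 after the first treatment.

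Section 7.0 (Statistics) gives one power statement. It begins "A total sample of 116 patients (58 Telephone, 58 Videoconference), measured at 3 time points". Power is put at 80% with alpha 0.05, and the purpose of the sample is described in these words: "to detect a 0.44 mean difference in Cancer Treatment Survey (CaTS) Procedural Concerns subscale scores between groups using a repeated measures design". As for the variance inputs, the section states: "The assumed standard deviation is 1.35, with a compound symmetry covariance structure and autocorrelation of 0.08". A 10% dropout allowance brings the target to 130.

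**The concern.** The two sections do not describe the same test. Section 4.1.1 sets three between-arm comparisons, one per visit. Section 7.0 powers a single between-arm difference that draws on all three measurements. Averaging three nearly uncorrelated measurements (correlation 0.08) cuts the variance to well under half that of one visit, so a sample size adequate for the average is far too small for any single visit.

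The averaged test has a fault of its own. One of its three measurements precedes the intervention, and under randomisation the expected difference there is zero. Including it dilutes whatever effect is present at T2 and T3.

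A reader of section 7.0 would conclude that a 0.44 difference after education will be detected four times in five. If that is not so, a null result would be over-interpreted. As long as no contrast is named, the protocol also leaves open which visit decides the trial.

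**Working it through.** **Inputs, all from section 7.0 unless noted.** Difference 0.44; SD 1.35 (1.80 × 0.75), so variance 1.8225; compound symmetry with correlation 0.08; 58 per arm; alpha 0.05. Allocation is 1:1 (section 4.2). The number of sides is not stated; two-sided is used because it reproduces the sample size.

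**Formulas (normal approximation).** V is the per-patient variance of the quantity compared.
- SE = √(2V/58)
- power = Φ(0.44/SE − 1.96)
- n per arm for 80% = 2V(1.960 + 0.842)²/0.44² = 2V × 7.849/0.1936

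**1. Reproducing the plan's figure: mean of all three visits.**
V = 1.8225 × (1 + 2 × 0.08)/3 = 0.7047; SE = 0.1559; 0.44/SE = 2.823. Power is 80.6% (79.9% with the noncentral t), and 57.1, so 58, per arm are needed. 58/0.9 = 64.4, so 65 per arm and 130 in total. Section 7.0 is reproduced. The same test one-sided would need 46 per arm, which does not match.

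**2. The comparison in section 4.1.1: one visit.**
V = 1.8225; SE = 0.2507; 0.44/SE = 1.755. Power is 41.9% (41.3% with the noncentral t), and 147.8, so 148, per arm are needed. Adjusting for T1 at correlation 0.08 multiplies V by 1 − 0.08² and raises power only to 42.1%.

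**3. The powered test when T1 carries no effect.**
If the true difference is 0 at T1 and 0.44 at both T2 and T3, the three-visit average is 0.44 × 2/3 = 0.293. With SE 0.1559 the ratio is 1.882 and power is 46.9%.

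**4. Mean of T2 and T3 only.**
- Unadjusted: V = 1.8225 × 1.08/2 = 0.9842; power 66.6%; 79.8, so 80, per arm needed.
- Adjusted for T1: V = 1.8225 × (1.08/2 − 0.08²) = 0.9725; power 67.1%; 78.9, so 79, per arm needed. Difference detectable with 80% power at 58 per arm: 2.802 × √(2 × 0.9725/58) = 0.513.

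**5. Sensitivity to the correlation** (0.3 and 0.5 are assumed values), 58 per arm, difference 0.44:

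| Contrast | 0.08 | 0.3 | 0.5 |
|---|---|---|---|
| Three-visit average | 80.6% | 67.1% | 57.5% |
| One visit, adjusted for T1 | 42.1% | 45.2% | 52.7% |
| T2/T3 average, adjusted for T1 | 67.1% | 65.0% | 69.9% |
| n per arm for 80%, T2/T3 adjusted | 78.9 | 82.8 | 73.9 |

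The last row peaks near a correlation of 0.25, at 83.1 per arm. No post-education contrast in the table reaches 80% at 58 per arm.

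**6. Type I error, conditional.** If significance at either T2 or T3 at unadjusted 0.05 counted as success, the error under bivariate normality would be 9.7% (9.1% at an assumed correlation of 0.5). The protocol permits that reading but does not state it.

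**The case against.** The best defence is that section 7.0 holds the only significance level and names a repeated-measures design, so it gives the confirmatory analysis, while section 4.1.1 only describes by-visit reporting. Section 4.1.1 contains no decision rule, and the model, covariates and multiplicity rule are ordinary content for an analysis plan that is not shown. That plan might name the contrast.

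Part of this stands. One cannot say that the deciding visit will be left open, only that this protocol does not fix it. The type I figure applies to a rule the protocol does not contain. Section 7.0 never uses the word average; the three-visit mean is inferred because the protocol has exactly three visits and, of the contrasts tried, only that one gives 58 per arm. The 46.9% assumes exactly 0.44 at both T2 and T3, whereas section 7.0 takes 0.44 from a single time point of an earlier study.

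The defence does not rescue the 80%. If section 7.0 is confirmatory, its test still includes T1 and is diluted. If section 4.1.1 governs, power is about 42%, whether the by-visit contrasts are separate tests or come from one model. No analysis plan can give 58 per arm 80% power for a 0.44 post-education difference on these inputs. A much higher correlation would help a T1-adjusted single visit (83% at an assumed 0.8), but that departs far from the stated 0.08 and would cut the three-visit average to 47%.

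It is also fair that the T2/T3 average is one choice among several. T2 alone or T3 alone would equally remove the contradiction, at lower power.

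**Conclusion.** The concern holds and should be corrected before any outcome is compared by arm. The arithmetic in section 7.0 is right for a three-visit average, but that is not the comparison in section 4.1.1, and one of its three visits precedes the intervention. For a 0.44 difference at 58 per arm, power is about 42% at T2 or T3 alone, about 67% for the T2/T3 average, and about 47% for the three-visit average when T1 carries no effect.

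These figures rest on SD 1.35, correlation 0.08, a two-sided 0.05 level and complete data on 58 per arm. If all 65 recruited per arm were analysed, a single visit would have about 46%. Across assumed correlations up to 0.5 the conclusion does not change.

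**What to change.** Amend section 4.1.1 to one primary contrast: the between-arm difference in CaTS-PC averaged over T2 and T3, from one repeated-measures model with T1 CaTS-PC as covariate, tested once at two-sided 0.05. Report the T2 and T3 differences with confidence intervals as supportive, and describe T1 by arm without a test. If the sponsor prefers a single post-education visit, the same amendment works, but section 7.0 must then state about 42%.

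Restate section 7.0 for the chosen contrast. For the T2/T3 average, keep 58 per arm analysed and 130 recruited, and state about 67% power for 0.44, or 80% for about 0.51. The questionnaires are already scheduled, so the cost is an amendment, a less favourable stated power, and visit-specific differences that become supportive.

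The alternative is to restore 80% for 0.44 with 79 per arm analysed: 158 in total, and 158/0.9 = 175.6, so 176 recruited. That is 46 more patients. At the planned rate of 130 in 7 months (18.6 per month) accrual would take about 9.5 months instead of 7. With a t-based calculation the figure is 80 per arm. Using the same structure for HADS-A is optional.

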#### 4.1.2 Secondary Endpoint(s)

##### 4.1.2a Anxiety Levels

Anxiety levels will be measured using the Hospital Anxiety and Depression Scale (HADS) anxiety subscale (HADS-A) at 3 time points, T1: baseline, T2: post CT-Simulation and T3: post RT day 1. Anxiety levels will be compared between the control and intervention groups at each time point.

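### The protocol treats T1 as an outcome visit and never as a baseline adjustment for T2 and T3; adjusting is a nearly free precision gain, negligible at its own correlation of 0.08 and sizeable only if the true correlation is higher

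*Protocol*

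**What the plan says.** Protocol 4.1.1 names the CaTS procedural concerns subscale at T1 (baseline), T2 (after CT simulation) and T3 (after the first treatment), and adds: "These measurements will be compared between the control and intervention group at each time point". Section 4.1.2a (Anxiety Levels) has the same structure for HADS-A: "Anxiety levels will be compared between the control and intervention groups at each time point".

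The Protocol Summary places T1 before the intervention: "Patients will be given a set of questionnaires prior to any education (T1"). The objective in 3.1.1 is whether videoconferencing is "more effective at reducing patient procedural fears and concerns".

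Section 7.0 sizes the trial on "A total sample of 116 patients (58 Telephone, 58 Videoconference), measured at 3 time points". The power claimed is 80% with alpha 0.05. The correlation is given together with the SD: "The assumed standard deviation is 1.35, with a compound symmetry covariance structure and autocorrelation of 0.08". The target is a difference of 0.44 points between arms in a repeated measures design. The correlation is said to have been estimated from a Cohen's d that the cited earlier trial reported at treatment completion.

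The protocol writes no analysis model. It mentions no covariate, no change score and no common baseline mean, for either scale.

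**The concern.** A score taken before education cannot show an effect of education, so comparing the arms at T1 answers none of the objectives. The same score is useful in another role. It is measured on the same patient and the same scale as T2 and T3, and conditioning on it removes the part of the later variance that it predicts, including the part of any chance T1 difference that persists. The protocol collects T1 from every patient but gives it the first role and not the second.

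What is at stake is precision in the primary comparison and in the HADS-A comparison. The amount depends on the within-patient correlation. The only value given, 0.08, was obtained indirectly from an effect size and not from repeated scores, so it is worth asking what happens if it is too low.

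**Working it through.** **Inputs (Protocol 7.0):** 58 per arm, SD 1.35, difference 0.44, alpha 0.05, compound symmetry, correlation r = 0.08. Sidedness is not stated; two-sided is assumed because it reproduces the plan's figure (one-sided gives 46 per arm). Values of r above 0.08 are assumptions and are shown as a range.

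**Step 1: reproduce the plan's sample size.** For the mean of m visits the variance factor is (1 + (m − 1)r)/m. With m = 3 and r = 0.08 it is 1.16/3 = 0.3867. Then

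n per arm = 2 × 1.35² × 0.3867 × (1.960 + 0.842)² / 0.44² = 57.1, rounded up to 58 (116 in total).

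With 10% dropout, 58/0.90 = 64.4, so 65 per arm and 130 in total. Both figures match. They match only with T1 counted as one of three outcome visits. The same formula gives 80 per arm for two visits and 148 for one. Section 7 therefore agrees with 4.1.1 on the role of T1.

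**Step 2: effect of adjusting for T1 on variance.** In units of SD²:
- One visit: unadjusted 1, adjusted 1 − r².
- Mean of T2 and T3: unadjusted (1 + r)/2. Its covariance with T1 is r, so adjusted (1 + r)/2 − r².

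At r = 0.08 the single-visit factor is 1 − 0.0064 = 0.9936, a fall of 0.6%. For the T2/T3 mean it goes from 0.5400 to 0.5336, a ratio of 0.988 and a fall of 1.2%.

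**Step 3: power for the T2/T3 mean** with 58 per arm, from the noncentral t distribution with the variances of Step 2:

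| r | Single-visit variance reduction | T2/T3 mean: factor unadjusted → adjusted | Reduction | Power unadjusted → adjusted |
|---|---|---|---|---|
| 0.08 (protocol) | 0.6% | 0.540 → 0.534 | 1.2% | 66% → 66% |
| 0.3 (assumed) | 9% | 0.650 → 0.560 | 14% | 58% → 64% |
| 0.5 (assumed) | 25% | 0.750 → 0.500 | 33% | 52% → 69% |
| 0.7 (assumed) | 49% | 0.850 → 0.360 | 58% | 47% → 83% |

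The normal approximation agrees to within about one percentage point (66.6% → 67.1% at 0.08; 52.7% → 69.9% at 0.5). In sample size at r = 0.08, adjustment moves the requirement from 80 to 79 per arm.

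**Step 4: chance T1 imbalance.** The standard error of the T1 difference between arms is 1.35 × √(2/58) = 0.251. What reaches an unadjusted later comparison is r times the imbalance:

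| r | Imbalance of one SE (0.25) | Imbalance at the 95% limit (1.96 × 0.251 = 0.49) |
|---|---|---|
| 0.08 | 0.02 | 0.04 |
| 0.3 | 0.08 | 0.15 |
| 0.5 | 0.13 | 0.25 |
| 0.7 | 0.18 | 0.34 |

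The target difference is 0.44.

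**HADS-A.** The documents give no SD, target difference or correlation for this scale, so no gain can be computed.

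**The case against.** The strongest objection is that the protocol does not call its comparison raw or unadjusted. Sections 4.1.1 and 4.1.2a are endpoint sections, no model is written, and covariates are commonly left to a statistical analysis plan, which is not shown here. That stands. A reader might infer that the protocol prescribes an unadjusted analysis, and the text does not go that far. What it does fix is the role of T1 as a compared time point in 4.1.1 and 4.1.2a, and as a third outcome visit in the calculation that yields 58 per arm. A later plan that uses T1 as a covariate would change that role.

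A second objection is that a repeated-measures model with T1 among the outcomes can still use it, through change from T1 or a common T1 mean. Neither is excluded, but neither is named, and they are not interchangeable. The single-visit variance factor for a change score is 2(1 − r), which is 1.84 at r = 0.08 and reaches 1.0 only at r = 0.5. Covariate adjustment, at 1 − r², never exceeds 1.

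Third, the harm all but vanishes on the protocol's own figures. This also stands: every material gain above comes from a correlation that the documents do not contain.

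Two further inferences should be resisted. The T1 standard error of 0.25 is 57% of the 0.44 target, but that describes the T1 difference itself; only r times it carries forward. Nor is the unadjusted contrast biased: randomisation protects it, and its standard error already allows for chance imbalance. The objective of reducing concerns can be answered validly without adjustment.

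Finally, the T2/T3 mean is not an estimand that the protocol states. It is used here to show the size of the effect, and the single-visit reductions do not depend on it.

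**Conclusion.** The point holds as a nearly free improvement in precision and not as an error. The protocol gives a pre-education score the role of an outcome and names no use of it as a baseline for T2 and T3. If r really is 0.08, adjustment gains about 1% of variance and no visible power. If r is 0.3 to 0.7, single-visit variance falls by 9% to 49%, and power for the T2/T3 mean rises by about 6 points at 0.3 (58% to 64%) and 36 points at 0.7 (47% to 83%). That range is an assumption. The case for acting is the asymmetry: adjustment costs almost nothing if 0.08 is right and recovers a good deal if it is too low.

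The unadjusted starting power of about 66% at r = 0.08 should not be put down to the lack of adjustment. It arises because the sample size relies on T1 as a third visit carrying the full difference. That is a separate issue, and adjusting for T1 does not repair it.

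**What to change.** In 4.1.1 and 4.1.2a (Anxiety Levels), replace the sentence on comparison at each time point with wording such as: T2 and T3 scores will be compared between arms in a longitudinal model that adjusts for the T1 score of the same scale; the adjusted difference will be reported with its 95% confidence interval; T1 scores will be summarised by arm descriptively.

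An acceptable alternative keeps T1 in the outcome vector with one mean common to both arms, which retains patients whose T1 is missing. Whichever form is chosen should be fixed before outcome data are seen by arm, so that adjusted and unadjusted results are not both available to choose from.

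The cost is one sentence in each section and one degree of freedom. No new data, visits or patients are needed. Section 7's treatment of T1 as an outcome visit has to be dealt with separately.
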